## C. Study Design and Research Methods

Potentially eligible subjects will be screened during routine clinic visits or over the telephone. Potentially eligible and interested subjects will return for informed consent and a screening/baseline visit. No research procedures will occur prior to consent, including the MOCA.

After obtaining informed consent, participants will undergo a graded exercise test to screen for potential underlying cardiovascular disease. V02 peak will be measured at this time to develop the exercise prescription. All participants will begin with a low intensity lead-in for 1-2 weeks, then advance to a moderate intensity exercise during first 12 weeks. Randomization to continue on moderate versus advance to high intensity will occur at week 13.

**1. Consent & baseline visit.** After obtaining consent, the participant will be evaluated

-After obtaining consent, the participant will be evaluated by

- medical history, physical examination including vital signs
- Montreal Cognitive Assessment (MOCA)
- Resting BP, 12-lead resting ECG, and then a graded exercise test (GXT) administered by research personnel and a clinician experienced in exercise stress testing of older adults ([name]) to screen out volunteers with evidence of ischemic heart disease, serious arrhythmias, or abnormal HR/BP responses to exercise. Briefly, the test will begin at a comfortable walking speed and 0% elevation; speed will be maintained and the grade increased by 2% every 2 min, until the participant reaches 85% of age-predicted maximal heart rate or the test is otherwise terminated. The absolute and relative indicators for terminating an exercise test that are recommended by the American College of Sports Medicine (ACSM) will be employed.
- Baseline physical function assessments will be administered.

**2. Procedure visit #1 (within 14 days of visit #1).** All participants will arrive between 7:30-8am for:

- DXA scan
- Vital signs
- Anthropometrics (waist/hip circumference)
- Blood draw (fasting)
- 36 (up to 46, if needed to ensure 36 paired biopsy samples) volunteer participants (18 HIV+/18 HIV-) will have a muscle biopsy
  - If muscle biopsy at the end of the study cannot be done (patient refuses, change in medications, etc), then the number of biopsies will increase to a maximum of 46 in order to ensure each group has at least 18 paired (entry/completion) biopsy samples.
- Questionnaires

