- Between the procedure #1 visit and the first exercise visit, participants will be sent home with an ActiWatch Spectrum monitor for activity and sleep.
- Between consent/baseline visit and procedure visit #1, patients will be sent home with a specimen cup with biosafety bag to collect stool and a 3 day dietary log. The log should be collected in real time during a 3 day time period preceding the procedure visit.
- Participants will be asked to collect stool within 72h period (if possible) prior to procedure visit #1 and place sample in a biosafety bag in their home freezer. They will bring the sample to procedure visit and it will be placed immediately in a -80C freezer within the RC2 11th floor lab.

**3. Exercise training.** The exercise intervention will begin at least 24 hours following, and within 14 days of the procedure visit (+/- 14 days for illness, scheduled vacation, etc).

- At the first visit, all participants will repeat physical function testing & 1-RM
- The first 2 weeks will be a lead-in period with low intensity exercise to gain familiarity with the machines. He/she will then be advanced to a moderate intensity exercise for an additional 10 weeks.
- During the exercise training, participants will come to the research center 3 to 4 days/week.
- Chair rise will be measured at the first visit of the week, every 2 weeks and pedometer data will be downloaded.
- To account for unforeseen absences from exercise (due to death of family/friends, illness, etc), the duration of exercise can be extended by up to 4 weeks. This will allow the participant to slowly acclimate back to the prior exercise intensity and minimize risk for injury. The exercise will only be extended if the participant is in agreement. If he/she wishes to complete the exercise intervention within the 24 weeks as planned, then the duration will not be extended.

4. **Acute inflammation visit 1.** At 3 time points during the study, participants will have an “acute exercise visit”.
  - The first will occur during week two of exercise
  - Participants will be asked to exercise on Monday, Thursday, and Friday.
  - **Thursday (beginning between 7:30-10am)** will consist of a high intensity CV + REx exercise stimulus, and a blood draw prior to exercise, and 0, 60, and 90 minutes following an exercise stimulus.

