**1. Muscle biopsy.** Subjects participating in the muscle biopsy portion will have a biopsy prior to beginning the exercise intervention and after completing the 24 week intervention. Subjects will be advised to refrain from any physical activity for at least 48 hours following the biopsy and return within 14 days of the screening/consent visit. Non-steroidal anti-inflammatories or aspirin are held for 7 days prior to the biopsy. If participants are taking direct oral anticoagulants, this will be held for 48 hours prior to the procedure (72 hours if creatinine clearance is 30-50 and taking dabigatran). Therapy can be resumed 24 hours after the procedure, or as instructed by their physician. At study completion, subjects will be asked to return within 7 days of the final exercise session for a muscle biopsy. The exercise intervention will begin >24 hours after the initial biopsy, but within 14 days. Participants will be asked to abstain from alcohol or caffeinated beverages after 1300h and to fast from any food or drink beginning at 9pm with the exception of water. Subjects will arrive at 8am in the CTRC for the biopsy. Percutaneous samples of the vastus lateralis muscle will be obtained. After cleansing the area of the thigh with antiseptic (e.g., chlorhexidine, Betadine solution), 1% lidocaine (without epinephrine) will be injected under the skin. A 3-5 mm incision will be made in the skin and fascia over the belly of the vastus lateralis, and 100-150 mg of muscle tissue will be removed using a Bergstrom side-cutting biopsy needle with suction applied. The incision will be closed and a compression wrap and ice will be applied to the incision area for 20 minutes. The patient will be given instructions for wound care before discharge.

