Sedentary time and sleep quality will be measured using two tools. Actiwatch Spectrum, accelerometers to collect physical activity and wake/sleep time through additional sensors for light and dark, will be worn for 1 week between the 1st procedure visit and the first exercise visit, and for 1 week between the week 24 and the procedure visit #2.

Accelerometers have been calibrated in [name] laboratory at Rush University, and data will be analyzed in conjunction with her laboratory. We will assess change in sedentary time and change in sleep using the actiwatch. The Pittsburgh sleep index and the Munich Chronotype will assess usual sleep habits and restfulness following sleep.

In addition, each participant will be provided with a pedometer (*Omron Tri-Axis USB Pedometer, HJ-324U*) to wear every day through the study to monitor overall activity patterns and changes with an exercise intervention. This monitor stores 22 days of data. The participant will be asked to bring the monitor every other week and data will be downloaded during the exercise session.

Evaluation of health status, medication use, and falls. A brief health status questionnaire will be completed by participants every 2 weeks to document potential study-related problems/concerns (e.g., exercise discomforts); changes in health status (e.g., hospitalizations), prescription and over-the-counter medications (including non-steroidal anti-inflammatory agents); and falls. The surveys will be reviewed by the study nurse and appropriate follow-up pursued.

Post-intervention follow-up. Participants will be contacted by phone 3 months following study completion. Continued frequency of exercise/physical activity (IPAQ), intent to continue exercising, overall well-being will be assessed.

Risk: A person with a very high depression score may be identified on the CES-D depression screening questionnaire.

Plans to minimize risk: CES-D questionnaires will be briefly reviewed prior to the study participant leaving the visit. If an individual indicates a risk for suicidal ideations or intent on the CES-D, the participant will be referred immediately to their primary care provider or the emergency room.

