Outcome measures will be available bi-weekly for chair rise, and three times for other functional measures. Serum IGF-I, IGFBP3, muscle IGF-1 mRNA/protein, visceral fat, LBM, and inflammatory cytokines will be measured at procedure visits #1 and #2. Secondary outcomes will include change in other cytokines and hormones, sleep quality, quality of life, V02 peak, strength, and modified SPPB. The inflammatory markers will be tested as mediators on the effect of exercise on changes in function and LBM. Additional secondary outcomes will determine if sedentary time increases as the physical activity intensity decreases, the impact of the intervention on the affect and efficacy of exercise. These factors will be important in design of larger interventions and dissemination to identify points of low exercise efficacy and poor affect and attempt to prevent drop-outs from the intervention. An important outcome is to ensure that intensive 3x/week physical activity does not lead to a decrease in usual activity and an increase in sedentary time due to exercise-related fatigue.

For the inflammatory analyses:

**Analysis.** We propose that no subjects in either arm will experience a major injury (e.g., muscle strain or other injury requiring self-prescribed or provider prescribed treatment) and no more than 1 subject in each group will drop out because of exercise-induced discomfort

(i.e., fatigue, muscle or joint pain). The step counts between arms will be compared to determine if the high-intensity group limits non-study activity. For Aim 3, we will compare the change between arms in IL-6, TNF $\alpha$  and sTNFRI (pre-exercise, and 0, 60, and 90 minutes, and 24 hours) with a single bout of exercise at weeks 2, 12, and 24. We also will compare relative changes in serum IL-6, TNF $\alpha$  and sTNFRI from week 2 to week 24 between groups using geometric means and 95% confidence intervals. Secondary outcomes will include the change in other inflammation (sTNFRII, hsCRP, IL-10) and immune activation (sCD14, sCD163) markers, change in physical function, QoL, depressive symptoms, and exercise self-efficacy between study arms. **Sample size and power.** Sample size calculations were conducted for the within and between group percent change in IL-6, TNF $\alpha$ , hs-CRP, and sTNFRI levels. Data from 49 HIV+ subjects with higher function were used to estimate sample size parameters. We anticipate additional power using

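### The baseline Actiwatch week can include post-biopsy rest days and the final week cannot, so the pre-post change can understate a later rise in sedentary time

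*Combined protocol and SAP*

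**What the plan says.** **Baseline wear.** Section IV.C, item 2, and Section IV.D.8 agree. The first states: "Between the procedure #1 visit and the first exercise visit, participants will be sent home with an ActiWatch Spectrum monitor". The second says the watch "will be worn for 1 week between the 1st procedure visit and the first exercise visit".

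**Baseline biopsy.** It is taken at procedure visit #1 (Section IV.C, item 2), where 36 "volunteer participants (18 HIV+/18 HIV-) will have a muscle biopsy". The number may rise to 46 to secure enough paired samples. Section IV.D.1 adds: "Subjects will be advised to refrain from any physical activity for at least 48 hours following the biopsy".

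**Start of exercise.** Section IV.C, item 3: "The exercise intervention will begin at least 24 hours following, and within 14 days of the procedure visit", with a further 14-day allowance for illness or travel.

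**Final wear and second biopsy.** The watch is worn again "for 1 week between the week 24 and the procedure visit #2" (Section IV.D.8). The second biopsy is taken at procedure visit #2, more than 48 hours after the last session (Section IV.C, item 9) and within 7 days of it (Section IV.D.1). Participants outside the biopsy subset may have procedure visit #2 on their last exercise day.

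**Use.** Section IV.D.8 assigns change in sedentary time and in sleep to the watch. Section IV.F says: "An important outcome is to ensure that intensive 3x/week physical activity does not lead to a decrease in usual activity", and names a rise in sedentary time through fatigue as part of the same worry.

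No section delays the baseline wear, drops the rest days, or adjusts for biopsy status.

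**The concern.** The two wear weeks sit on opposite sides of a biopsy. At baseline the watch goes on after it; at the end the watch comes off before it. In biopsied participants, the change score can therefore set a week containing advised inactivity against a week without it. If the rest days add sitting time, baseline is too high and a later rise looks smaller than it is. Sleep change could be affected in the same way.

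The direction matters because the plan's question is whether training displaces usual activity. Everyone exercises and there is no untrained control group, so that question rests on within-person change, which is where the asymmetry acts. The error runs towards false reassurance. Sections IV.A and IV.G also use sedentary time to judge whether high-intensity exercise is detrimental or durable.

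**Working it through.** The plan gives no figure for this measure, so there is nothing to reproduce. The check is the visit order, followed by a bounded calculation.

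**Inputs from the plan**
- Participants: 36 HIV+ and 36 HIV-, 72 in all (Section IV.F).
- Biopsied at baseline: 36, up to 46 (Section IV.C, item 2).
- Advised rest: at least 48 hours, i.e. 2 days at the minimum (Section IV.D.1).
- Wear: 7 days (Section IV.D.8).

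**Assumption.** x = extra sedentary hours on each rest day. The documents give no value; I use 0.5 to 4.

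**Step 1. Share biopsied.** 36/72 = 50%; 46/72 = 64%.

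**Step 2. Share of the week affected.** At most 2/7 = 29% for the minimum rest period, if wear begins on the day of biopsy. It is 0 if wear begins after the 48 hours.

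**Step 3. Inflation of the baseline daily mean.**
Biopsied participants: 60 × x × 2/7 min/day. Whole sample: multiply by the share biopsied.

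| x (h per rest day) | Biopsied (min/day) | All 72, 36 biopsied | All 72, 46 biopsied |
|---|---|---|---|
| 0.5 | 8.6 | 4.3 | 5.5 |
| 1 | 17.1 | 8.6 | 11.0 |
| 2 | 34.3 | 17.1 | 21.9 |
| 4 | 68.6 | 34.3 | 43.8 |

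With only one rest day inside the recording, each entry halves.

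**Step 4. Group contrasts.**
- HIV status: the planned 18 v 18 gives an expected bias near 0.
- Intensity: randomization at week 13 balances biopsy status in expectation. Allocating 72 participants, 36 of them biopsied, at random to two arms of 36 gives a hypergeometric SD of about 2.1 biopsied per arm, with a central 95% range of 14 to 22. At 22 v 14 and x = 2, the between-arm shift is (22 − 14)/36 × 34.3 = 7.6 min/day.

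**Step 5. Does the week fit?** If exercise starts d days after procedure visit #1, at most d days of wear are available. The permitted minimum, 24 hours, leaves 1 day. Any start before day 7 shortens the recording. A shortened recording also carries a larger share of rest days: 2/4 for a 4-day wear, against 2/7.

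**Step 6. The final window.** For biopsied participants, the interval after the last session runs from just over 2 days to 7 days. For the others it may be 0 days. The final week is thus not the same period in the two subsets.

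**The case against.** The strongest reply is that the overlap is permitted but not required. The plan asks for one week between two visits and does not say that wear starts on the day of biopsy. With up to 14 days before exercise, the week could start after the rest period. Participants are also sedentary by entry criterion, so two days without activity may add little sitting time, and x could be near zero. Both points stand: the inflation is an inference, not an established fact.

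It can also be said that self-reported sedentary time (IPAQ, seven time points) and a daily pedometer do not depend on this week. That is true, but neither replaces the watch: one is self-report, the other counts steps, and the plan specifies no pre-training step-count week. In addition, the gap of more than 48 hours without exercise before the second biopsy may lower activity in the final week and partly offset the asymmetry.

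A reader might infer three stronger things that the documents do not support:
- *That the design hides any later rise.* The bias is bounded. It could cancel a rise of its own size or smaller, but would only shrink a larger one.
- *That training days contaminate the baseline recording.* Sections IV.C and IV.D.8 both end the wear before the first exercise visit. An early start shortens the recording instead.
- *That the HIV and intensity comparisons are biased.* A shared offset largely cancels under the 18/18 split and randomization.

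**Conclusion.** The point holds for the within-person change. As scheduled, the baseline week can include the advised rest days in half or more of the participants and the final week cannot. Nothing in the plan prevents or corrects this. The expected direction is an overstated baseline and an understated later rise. On the assumed 0.5 to 4 hours per rest day, with both days inside a full week, the inflation is about 9 to 69 min/day in biopsied participants and 4 to 44 min/day overall. It is zero if wear happens to start after the rest period.

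Two schedule conflicts need no assumption about the biopsy's effect. A 24-hour start leaves no room for a week of wear. For biopsied participants, the 24-hour minimum start and the 48-hour advice do not agree and must be reconciled.

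This concerns a secondary measure, not chair rise. It merits correction because the plan itself calls the outcome important and the change is cheap.

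**What to change.** 1. Issue the Actiwatch at the consent/baseline visit with the stool kit and diet log. Have it worn for 7 days starting the day after the exercise test, so that the test does not disturb the recording. Collect it at procedure visit #1 before the biopsy. Alternatively, start wear only after the advised rest period and complete 7 days before the first exercise visit.
2. For records already collected (Section II mentions 15 HIV-infected participants enrolled), exclude the post-biopsy rest days. With full overlap, 5 of 7 days remain.
3. Define the final wear week identically for biopsied and non-biopsied participants, and state where it lies relative to the last training session. Moving the baseline week alone does not settle this.
4. Reconcile the 24-hour start in Section IV.C, item 3 (repeated in Section IV.D.1) with the 48-hour advice in Section IV.D.1.

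**Cost.** A few schedule lines, with no extra visit. Under the first option, procedure visit #1 must fall at least about 8 days after consent (1 + 7), which is within the 14 days allowed, and a few watches will go to people later found ineligible.

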## **2. Potential Scientific Problems:**

The primary problem that we anticipate is difficulty with enrollment. As of 10/30/2014, the HIV clinic at the University of Colorado cares for 724 HIV+ adults aged 50 or older. Thus, we do not anticipate that enrollment will be a significant barrier. However, we will plan to advertise the study at additional venues including HIV patient advocacy groups (On the TEN), the AIDS Education and Training Center twice year updates (for HIV providers, social workers, advocates), and encourage word-of-mouth advertising. If recruitment appears to be lagging significantly, we will addend our proposal and expand recruitment at the Denver Health HIV clinic. By targeting recruitment at HIV- controls, we will try to maintain similar demographic characteristics between the HIV+ and HIV- groups. Additionally, we limited our enrollment criteria with BMI restrictions—if we have difficulty recruiting due to a larger proportion of participants with a BMI <24, we may choose to enroll lower BMI, and then target recruitment of the HIV- to include participants with a lower BMI.

Other problems that we anticipate: lack of adequate sample on muscle biopsy due to low baseline muscle mass. The primary outcome will only require minimal muscle sample (IGF-1 protein and mRNA). Thus, we recognize that all muscle analyses may not be able to be completed, but will target the studies on the primary analyses of interest.

## **F. Data Analysis Plan:**

### **Statistical Considerations**

Sample Size Calculations: The primary outcome for sample size calculations is change from baseline in chair rise pace. We assume a change from baseline of 1.5 (SD=1.54) seconds or larger, based on differences observed by fall history [85]: Sample sizes of 36/group will yield an estimate of 29 patients per group at week 16 (~20% dropout). 29 subjects per group achieves over 80% power to detect a between group difference of 1.5 seconds with a significance level of 0.05 and the standard deviation conservatively estimated at 2.0 seconds[110] using a two-sided two-sample equal variance t-test.

Matching and Randomization: Enrollment in the uninfected arm will be constrained to lag behind HIV-enrollments. Upon the enrollment of every 5th HIV-infected patient, HIV-uninfected enrollment will be evaluated and recruiting goals updated to ensure a similar age (<60; >=60), gender, BMI, and smoking

distribution. Given the smaller proportion of women in the HIV-infected population, we plan to enroll fewer women. The randomization will be blocked by gender and exercise intensity to ensure balance according to the following scheme:

Exercise Intensity	Moderate (N=36)		High (N=36)	
HIV-Infected (N=36)	Men:	15	Men:	15
	Women:	3	Women:	3
Controls (N=36)	Men:	15	Men:	15
	Women:	3	Women:	3

**Analysis Plan:** Given repeated measurements over time, a linear mixed effects model will be used with change from week 0 as the primary outcome. The inclusion of additional time points will provide additional power. Groups defined by HIV-status (Exercise Intensity) will be evaluated. The baseline value and a group and time interaction term will be included as model predictors. The primary analysis will be intent to treat. Baseline (week 0) characteristics will be compared between groups prior to comparisons of endpoints, with log transformation for normality, as appropriate. The primary analysis will consider adjusting for age, smoking, exercise intensity (HIV-status) and body mass index (BMI); although if matching and/or balance by group is achieved, they may be precision variables, but they cannot be confounders. Finally, given the potential for non-ignorable dropout, we will accommodate dropout in the analysis of functional measures using a semi-parametric varying-coefficient model approach [150]. The primary analyses will assume that the slope beyond dropout is linear with sensitivity analyses utilizing a slope is attenuated by 50% and a zero slope beyond dropout, the latter being similar to a last value carried forward. Additionally a sensitivity analysis using only data from study completers will be conducted.

Change in IGF-I mRNA will be a primary outcome in the subset of participants undergoing muscle biopsy.

Outcome measures will be available bi-weekly for chair rise, and three times for other functional measures. Serum IGF-I, IGFBP3, muscle IGF-1 mRNA/protein, visceral fat, LBM, and inflammatory cytokines will be measured at procedure visits #1 and #2. Secondary outcomes will include change in other cytokines and hormones, sleep quality, quality of life, V02 peak, strength, and modified SPPB. The inflammatory markers will be tested as mediators on the effect of exercise on changes in function and LBM. Additional secondary outcomes will determine if sedentary time increases as the physical activity intensity decreases, the impact of the intervention on the affect and efficacy of exercise. These factors will be important in design of larger interventions and dissemination to identify points of low exercise efficacy and poor affect and attempt to prevent drop-outs from the intervention. An important outcome is to ensure that intensive 3x/week physical activity does not lead to a decrease in usual activity and an increase in sedentary time due to exercise-related fatigue.

For the inflammatory analyses:

**Analysis.** We propose that no subjects in either arm will experience a major injury (e.g., muscle strain or other injury requiring self-prescribed or provider prescribed treatment) and no more than 1 subject in each group will drop out because of exercise-induced discomfort

(i.e., fatigue, muscle or joint pain). The step counts between arms will be compared to determine if the high-intensity group limits non-study activity. For Aim 3, we will compare the change between arms in IL-6, TNF $\alpha$  and sTNFRI (pre-exercise, and 0, 60, and 90 minutes, and 24 hours) with a single bout of exercise at weeks 2, 12, and 24. We also will compare relative changes in serum IL-6, TNF $\alpha$  and sTNFRI from week 2 to week 24 between groups using geometric means and 95% confidence intervals. Secondary outcomes will include the change in other inflammation (sTNFRII, hsCRP, IL-10) and immune activation (sCD14, sCD163) markers, change in physical function, QoL, depressive symptoms, and exercise self-efficacy between study arms. **Sample size and power.** Sample size calculations were conducted for the within and between group percent change in IL-6, TNF $\alpha$ , hs-CRP, and sTNFRI levels. Data from 49 HIV+ subjects with higher function were used to estimate sample size parameters. We anticipate additional power using

Table 3. Detectable % change from geometric mean needed to achieve 80% power

Outcome	Geometric Mean	Mean (SD) log scale	Within Group Change*		Between Groups Change	
			Increase	Decrease	Increase	Decrease
IL-6 (pg/mL)	0.98	-0.025 (0.629)	52%	34%	110%	52%
TNF $\alpha$ (pg/mL)	1.48	0.392 (0.274)	20%	17%	37%	28%
hs-CRP (mg/L)	1.55	0.440 (1.21)	120%	55%	300%	75%
sTNFRI (pg/mL)	997.9	6.91 (0.25)	24%	19%	34%	25%

\*standard deviation (SD) adjusted based on a 0.7 correlation between paired measurements.

the summary measure AUC. Table 3 contains the within and between group detectable percent change from the geometric mean was calculated assuming a sample size of 13 subjects per group, 80% power, a significance level of 0.05 and a two-sided two-sample t-test.

For the qualitative interviews:

Data Analysis: We will analyze transcribed interviews using a mixed inductive and deductive approach. To develop the codebook, a qualitative analyst and the PI will code a subset of interviews separately using ATLAS.ti software. Coding differences will be adjudicated by [name] (Co-I). The analyst will then code the remainder of the interviews. After open coding, key meanings and insights will be identified and then reduced to identify patterns. Themes will be explored and tested using iterative techniques across subsequent individual and group level interviews.

